In November 2007, we received a research grant from ZonMw to conduct a pharmacotherapeutic study, in which we planned to investigate, in three separate randomized controlled feasibility trials, the effectiveness of topiramate, modafinil, and sustained release (SR) dexamphetamine in the treatment of crack-cocaine dependent patients. On February 24, 2010 the Medical Ethical Committee of the AMC approved our study protocol "New pharmacotherapeutic treatment options for crack-cocaine dependent patients in the Netherlands" (MEC 09/197 # 11.17.0029)

At the time of this writing (October 2013), the data pertaining to the studies on topiramate and modafinil have largely been collected. For the feasibility study on dexamphetamine SR, in which we are ready to start patient recruitment, we recently submitted a substantial amendment to the medical ethical committee of the AMC. On September 13, 2013, the MEC informed us that the proposed changes in the study protocol of the dexamphetamine SR study were too substantial to be considered an amendment, and that, instead, this protocol should be submitted to the MEC as a new project. In the present protocol, the dexamphetamine SR study is described as a new project.

BACKGROUND AND RATIONALE OF THE STUDY

Cocaine, particularly in its base form ('crack'), has become one of the drugs of most concern in the Netherlands, being associated with a wide range of medical, psychiatric and social problems for the individual, and with significant public order consequences for society. Despite this status as one of the most problematic addictions, available treatment options for cocaine dependent patients are limited at best. To date, there are no proven effective pharmacotherapies for cocaine dependence (De Lima et al., 2002; O'Brien, 2005; Kampman et al., 2005; Dürsteler-MacFarland et al., 2013), despite the wide range of medications tested for this specific type of dependence, including: direct and indirect agonists (Amato et al., 2011; Pérez-Maná et al., 2011), antidepressants (Pani et al., 2011), antipsychotics (Amato et al., 2007), anticonvulsants (Minozzie et al., 2008; Alvarez et al., 2010), psychostimulants (Castells et al., 2010), and disulfiram (Pani et al., 2010). In addition, psychosocial interventions for cocaine dependence have generally produced modest results (Knapp et al., 2007; Shearer, 2007). From these, one of the more promising interventions – contingency management – has recently been investigated in the Netherlands by our research group in the context of the medical prescription of heroin to chronic heroin dependent patients with concurrent cocaine use. In this study (the results of which are yet to be published), we found that contingency management resulted in significant but small reductions in cocaine use (Blanken et al., in preparation).

Given the limited success of psychosocial interventions and lack of proven effective pharmacological treatment options, the testing of new medications for cocaine dependence should be high on the research agenda. In this testing program, two basic pharmacological strategies can be distinguished, one directed at substantial reduction or total abstinence from all stimulants and the other directed at the replacement of illegal, short-acting stimulants that are smoked (i.e. crack-cocaine) or injected by medically prescribed, long-acting stimulants that can be taken orally. Concerning the first strategy, the anticonvulsant topiramate and the alpha-adrenergic/glutamate agonist modafinil are currently under investigation in the context of the wider pharmacotherapeutic study of our research group (see Preface). Concerning the second strategy, a growing number of pre-clinical and human studies suggest that the monoamine releaser dexamphetamine should be the prime candidate for replacement therapy (Grabowski et al., 2004a; Castells et al., 2010; Van den Brink 2012). Several controlled studies have shown significant improvements in treatment retention and reduced cocaine use in cocaine addicts receiving sustained release dexamphetamine (Grabowski et al., 2001; Grabowski et al., 2004b; Shearer et al., 2003), without serious adverse events (including no serious cardiovascular complications).

Hence, the pharmacotherapy proposed in the present study will consist of sustained release dexamphetamine. The basic rationale for substitution treatment for cocaine dependence is similar to that for other addictions: it aims to replace uncontrolled and harmful drug use with regulated and safer use, in terms of dose, route of administration and adverse effects, and it facilitates engagement with health care services by attracting and retaining addicted individuals in treatment (Shearer & Gowing,

2004). In addition, the regular supervised prescription regimen may by itself help the patient to structure his daily life. Oral application of sustained release dexamphetamine, with a much slower onset and limited peak effect than crack-cocaine, clearly meets the rationale for substitution treatment. As in any medication study, the primary focus of our study will be on the balance between (potential) benefit and harm produced by the medication, taking into consideration the personal and societal damage associated with continued illicit use of cocaine, in a situation without effective pharmacological treatment options.

STUDY OBJECTIVE

The overall objective of this feasibility study is to investigate the usefulness of sustained release dexamphetamine in the treatment of cocaine dependence, and – dependent upon the results of both this study and the parallel studies of topiramate and modafinil (see Preface) – to yield one or more candidate medications for future investigation in a large-scale confirmatory controlled trial. Specifically, the study aims to evaluate, in crack dependent patients with comorbid heroin dependence, the response to medically prescribed oral dexamphetamine SR (60 mg/day) as an add-on to heroin-assisted treatment, in terms of potential efficacy, acceptance, compliance, safety, and patient satisfaction.

GENERAL STUDY DESIGN

The study will be conducted using a multicenter, double-blind, placebo-controlled, randomized treatment design. Following screening and baseline assessment, eligible patients in a heroin-assisted maintenance treatment program will be randomly allocated (ratio: 1:1) by the collaborating pharmacist to (continued) heroin-assisted treatment plus 12 weeks treatment with placebo (control group; n=36) or to (continued) heroin-assisted treatment plus 12 weeks treatment with sustained release dexamphetamine 60 mg/day (experimental group; n=36). Randomization will be concealed, using a computer-generated randomization list, and will be prestratified by treatment center (4 treatment centers). Study assessments will take place at baseline, and 4, 8, and 12 weeks after baseline. The primary time point at which treatment outcome will be determined is 12 weeks after baseline.

4. For reasons of both medical and public order safety, and given that sustained release dexamphetamine is not (yet) a registered medication in the Netherlands and is subject to the Dutch Opium Act, it is important that the present study will be conducted in a treatment setting with ample – treatment and research – experience in using strict safety procedures with respect to the storage, staff-supervised prescription, and prevention of diversion of a controlled study medication, monitoring of adverse and serious adverse events, and drug accountability. Given their extensive experience with prescribing diacetylmorphine to heroin dependent patients, heroin-assisted treatment programs are fully equipped to meet these requirements.

Against this background, we propose to evaluate the effectiveness of sustained release dexamphetamine in heroin dependent patients with comorbid crack-cocaine dependence in a heroin-assisted treatment program.

Study participants

Study participants will be recruited from the population of patients who already receive (ongoing) heroin-assisted treatment in the designated treatment programs in The Hague, Rotterdam and Amsterdam. To qualify for heroin-assisted treatment, patients must meet a set of well-defined selection criteria pertaining to the situation prior to the start of heroin-assisted treatment, which include that the patient must be at least 25 years old, and have a treatment-resistant heroin dependency, as indicated by (a) a history of heroin dependence (DSM-IV) of at least five years, (b) a minimum dose of 50 mg/day (patients who inhale their heroin) or 60 mg/day (patients who inject their heroin) of methadone for an uninterrupted period of at least 4 weeks in the previous 5 years, (c) a history of regular treatment contacts with the methadone program in the previous 6 months, (d) a history of unsuccessful methadone maintenance treatments, (e) daily or nearly daily use of illicit heroin, and (f) poor physical, mental or social functioning (Van den Brink et al., 2003). It is important to note that these selection criteria for participation in heroin-assisted treatment pertain to the situation prior to the start of heroin-assisted treatment, which for most patients is (far) more than a year ago.

To be eligible for the present study, patients must:

1. be at least 25 years old;
2. be cocaine dependent (DSM-IV) during at least the previous 5 years;
3. use cocaine on a regular basis (i.e., ≥ 8 days) in the previous month;
4. administer their cocaine primarily by means of basing ('crack');
5. have a history of earlier failed treatments aimed at reducing, or abstaining from, cocaine use ('treatment-refractory'). In order to qualify as 'treatment-refractory', the patient must have had at least two earlier treatment episodes targeted at reduction of cocaine use, yet still be cocaine dependent in the previous year, and use cocaine on a regular basis in the previous month;
6. be able and willing to participate in the study treatment and assessments;
7. have provided written informed consent.

Patients will be excluded in case of:

1. severe medical (e.g., severe renal or kidney insufficiency/failure, hypertension, glaucoma) or psychiatric problems (e.g., acute psychosis or history of drug-induced psychotic disorder, acute suicidality), which constitute a contraindication for participation;

2. cardiovascular problems (ECG);
3. (desired) pregnancy or continued lactation;
4. anticipated necessity of inpatient treatment (clinical judgement);
5. insufficient command of the Dutch language;
6. current participation in another addiction treatment trial.

STUDY TREATMENTS

As described before, study participants will be recruited from the population of patients who already receive (ongoing) heroin-assisted treatment for their concurrent heroin dependency. Hence, heroin-assisted treatment will be the underlying treatment (“treatment as usual”) for all patients, in both the control and experimental group. In heroin-assisted treatment, patients have the possibility to receive – dependent upon their usual route of heroin administration – oral or injectable heroin (pharmaceutical grade diacetylmorphine; max. single dose 400 mg; max. daily dose 1000 mg) three times a day (morning, afternoon, evening), during seven days a week in designated treatment centers, and oral methadone once a day (max. daily dose 150 mg). Both heroin and methadone have to be taken under supervision at the treatment site. On a yearly basis, the treating physician and other treatment staff evaluate whether continuation of heroin-assisted treatment is indicated, based on the patient’s health and social functioning. Diacetylmorphine was registered in the Netherlands for the treatment of chronic, treatment-resistant heroin dependence in December 2006, and has since then been prescribed for this indication in 17 designated treatment programs throughout the Netherlands.

Control treatment consists of ongoing heroin-assisted treatment (as described above) plus 12 weeks treatment with placebo. Placebo (2 tablets/day) will be matched to sustained release dexamphetamine tablets, and will be dispensed once daily during the patient’s morning visit at the treatment center. For the purpose of the present study, the placebo tablets were manufactured by the Slotervaart pharmacist (group of [name]), in compliance with the principles and guidelines of good manufacturing practice (see appendix: IMP-dossier, July 2013).

Experimental treatment consists of ongoing heroin-assisted treatment (as described above) plus 12 weeks treatment with sustained release dexamphetamine sulfate, prescribed in a fixed, single oral dose of 60 mg/day (2 tablets of 30 mg each). Oral sustained release dexamphetamine dose-levels of 30-60 up to 110 mg/day have been used in several studies in methamphetamine (Galloway et al., 2011; Longo et al. 2010) and cocaine dependent (Grabowski et al., 2001, 2004b) patients. In addition, oral dexamphetamine is prescribed to amphetamine users with heavy, problematic use in the United Kingdom at doses ranging from 5-200 mg/day (Bradbeer et al., 1998). Sustained release dexamphetamine has an average elimination half-life of approx. 12 hours, will be dispensed once daily during the patient’s morning visit at the treatment centre, and – to allow intensive safety monitoring – must be taken under supervision at the treatment site. In addition, weekly assessments of heart rate and blood pressure will be conducted during the entire study period of 12 weeks. For the purpose of the present study, sustained release dexamphetamine sulfate tablets of 30 mg each were manufactured by the Slotervaart pharmacist (group of [name]), in compliance with the principles and guidelines of good manufacturing practice (see appendix: IMP-dossier, July 2013).

In case a patient terminates his/her study treatment before week 12, or is withdrawn from the study for medical reasons, he/she will not be replaced by another patient. Following the end of the 12 weeks trial period, patients will continue their heroin-assisted treatment, but the study medication (either placebo or sustained release dexamphetamine; due to blinding unknown to both the treatment physician and research staff) will be terminated in all patients, and all usual treatment options in Dutch addiction care will be available to the patients, if indicated.

STUDY MEDICATIONS

Safety profile

Sustained release dexamphetamine sulfate

For the purpose of the present study, sustained release dexamphetamine sulfate tablets of 30 mg each were manufactured by the Slotervaart pharmacist (group of [name]), in compliance with the principles and guidelines of good manufacturing practice (see appendix: IMP-dossier, July 2013).

In the United States, sustained release dexamphetamine sulfate is marketed under the brand name Dexedrine® (Spansule capsules), for the treatment of ADHD and narcolepsy. The study medication in the present trial contains the same active ingredient – dexamphetamine sulfate, prescribed in sustained release form – and has a similar dissolution profile as Dexedrine® (see appendix: IMP-dossier, July 2013). The Medication Guide for Dexedrine® (see link below) summarizes the following possible side effects (adverse reactions) for sustained release dexamphetamine sulfate:

Cardiovascular:	Palpitations, tachycardia, elevation of blood pressure. There have been isolated reports of cardiomyopathy associated with chronic amphetamine use.
Central nervous system:	Psychotic episodes at recommended doses (rare), overstimulation, restlessness, dizziness, insomnia, euphoria, dyskinesia, dysphoria, tremor, headache, exacerbation of motor and phonic tics, and Tourette's syndrome.
Gastrointestinal:	Dryness of the mouth, unpleasant taste, diarrhea, constipation, other gastrointestinal disturbances. Anorexia and weight loss may occur as undesirable effects.
Allergic:	Urticaria.
Endocrine:	Impotence, changes in libido.

Source: <http://dailymed.nlm.nih.gov/dailymed/lookup.cfm?setid=18b7c145-3e8f-4e7e-c6b5-080d4139a008>, accessed at 2013-09-25.

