Given the described safety profile of sustained release dexamphetamine sulfate preparations, the few (serious) adverse events and mild and often transient adverse reactions observed in studies in stimulant dependent patients, and since the patients in the present study will be thoroughly screened (medical screening, including blood pallet and ECG at baseline and 12 weeks follow-up) and monitored ((S)AEs weekly; heart rate and blood pressure weekly), with medication intake under direct supervision of the treatment centers' medical staff, safety risks are expected to be small and manageable.

Placebo

For the purpose of the present study, the placebo tablets were manufactured by the Slotervaart pharmacist (group of [name]), in compliance with the principles and guidelines of good manufacturing practice (see appendix: IMP-dossier, July 2013). The placebo tablets are identical in shape, color, and content to the sustained release dexamphetamine tablets, with the exception of the active ingredient – dexamphetamine sulfate – which is replaced by an equal amount of lactose monohydrate in the placebo tablets.

Drug accountability

Study medication will be supplied by the central pharmacy to the local treatment centers. Upon receipt, the local treatment center will store the study medication in a safe. Each study center will keep full record per patient of the study medication dispensed on a daily basis. These records will be periodically checked by independent monitors from the AMC hospital pharmacy. The study medication has to be taken under supervision of the treatment staff at the treatment site. Any unused study medication must be accounted for, and documented, by the local treatment center, and will be desctructed according to the procedures developed by the AMC hospital pharmacy.

ASSESSMENTS

In both the control and experimental group, study assessments will take place at baseline, and 4, 8, and 12 weeks after baseline (see Table 1. Overview of assessments and instruments). The assessments will be conducted by trained research-assistants who are independent from the treatment staff, using standardized instruments to minimize information bias. At baseline, the treating physician will conduct a thorough medical examination to determine whether the patient should be excluded from the study due to the presence of contraindications.

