At baseline, the following self-report instruments will be administered: the Composite International Diagnostic Interview Substance Abuse Module (CIDI-SAM; cocaine and alcohol dependence; Cottler, 2000), as well as questions on suicidal risk from the MINI International Neuropsychiatric Interview (MINI; Sheehan et al., 1998); the short version of the Addiction Severity Index (ASI; McLellan et al., 1980, 1992; Hendriks et al., 1989), supplemented with questions about current illegal activities, income, and living arrangements (similar to the ASI-version used in the CRF of the Dutch RCT on medically prescribed heroin); the Time Line Follow-Back (TLFB, pertaining to cocaine use in the previous month; Sobell & Sobell, 1992); the Maudsley Addiction Profile-Health Symptoms Scale (MAP-HSS; Marsden et al., 1998); the Symptoms Check List-90 (SCL-90; Derogatis et al., 1993; Arrindel & Ettema, 1996); the Obsessive Compulsive Drug use Scale (OCDS; Anton et al., 1996; De Wildt et al., 2005), the EuroQol (EQ-5D; Brooks, 1996), and the Readiness to Change Questionnaire (RCQ; Defuentes-Merillas et al., 2002).

At the 12 weeks assessment, (follow-up versions of) each of these instruments will be administered again, with the exception of the CIDI, MINI and RCQ. In addition, patient satisfaction (Client Satisfaction Questionnaire; CSQ-8; De Wilde & Hendriks, 2005), supplemented with questions pertaining to the received medication (placebo or sustained release dexamphetamine) will be assessed.

At the 4 and 8 weeks assessment, the TLFB (pertaining to cocaine use in the previous month) and the ASI-items pertaining to other substance use will be administered, as well as the MAP-HSS, SCL-90, OCDS, and EQ-5D.

Additional assessments include blood sampling (laboratory screen: BSE, MCH, MCV, MCHC, GGT, ALAT, ASAT, alkalase phosphate, leucocytes, thrombocytes) (screening/baseline assessment and 12 weeks assessment; 2 x 16 ml), ECG (screening/baseline assessment and 12 weeks assessment), weekly medical screening; weekly check on heart rate and blood pressure during the entire study period; two times/week urine sampling (cocaine metabolites) during the 4 weeks preceding the 12 weeks assessment; monthly pregnancy testing (females); weekly registration of adverse events, serious adverse events (see: Safety reporting), and co-medication; study drug accountability (placebo and sustained release dexamphetamine); treatment compliance.

OUTCOME MEASURES AND DATA ANALYSIS

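### Severe kidney failure is a named exclusion, but no scheduled test measures kidney function; creatinine with eGFR could be added to the screening blood already drawn

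*Protocol*

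**What the plan says.** Exclusion criterion 1 (STUDY POPULATION, Study participants) rules out severe medical or psychiatric problems that are a contraindication to taking part. Its medical examples are "severe medical (e.g., severe renal or kidney insufficiency/failure, hypertension, glaucoma". Criterion 2 names its own test: "cardiovascular problems (ECG".

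The ASSESSMENTS section states who applies these criteria. At baseline "the treating physician will conduct a thorough medical examination to determine whether the patient should be excluded from the study" on account of contraindications. The content of that examination is not described. The same section itemises the blood tests, drawn at screening/baseline and at week 12 (16 ml each time): "laboratory screen: BSE, MCH, MCV, MCHC, GGT, ALAT, ASAT, alkalase phosphate, leucocytes, thrombocytes". Urine is collected for cocaine metabolites, and women have pregnancy tests.

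Under STUDY MEDICATIONS, Safety profile, the Protocol concludes that the safety risks should be small and manageable. One of its reasons is that patients will be "thoroughly screened (medical screening, including blood pallet and ECG at baseline and 12 weeks follow-up".

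**The concern.** The Protocol treats severe kidney failure as a reason not to give the study drug, yet it schedules nothing that would show it. The blood panel is a closed list of haematology and liver-type tests, so a renal marker cannot be assumed to be included. The safety argument leans on that same panel, which says nothing about an organ failure the Protocol itself chose as an example of a contraindication.

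At stake is whether the treating physician can apply the criterion on a measurement, or must rely on history and clinical impression. The dose is fixed at 60 mg/day, so screening is the point at which a renal contraindication would be acted on.

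**Working it through.** This is a comparison of the exclusion criteria with the scheduled assessments. The only arithmetic is counting.

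**Step 1. Laboratory panel (ASSESSMENTS).**
- Haematology and sedimentation rate: BSE, MCH, MCV, MCHC, leucocytes, thrombocytes = 6.
- Liver-type enzymes: GGT, ALAT, ASAT, alkaline phosphatase (misspelt in the Protocol) = 4.
- Total 6 + 4 = 10. Creatinine, eGFR, urea and cystatin C are all absent, so 0 of 10 measure kidney function.

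**Step 2. Other scheduled tests (ASSESSMENTS and Table 1).** These are ECG, heart rate and blood pressure, pregnancy testing, and urinalysis for cocaine metabolites. None measures kidney function.

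**Step 3. Physical conditions named in exclusion criteria 1 to 3, against the baseline column of Table 1.**

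| Condition | Baseline measurement |
|---|---|
| Hypertension | Blood pressure |
| Cardiovascular problems | ECG |
| Pregnancy | Pregnancy test |
| Severe kidney failure | None |
| Glaucoma | None |

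Three of these five are measured and two are not. The table leaves out the psychiatric examples in criterion 1 and lactation in criterion 3, which are normally settled by history or interview. Of the two unmeasured conditions, only kidney function can be read from the blood sample already planned.

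**Step 4. What else could reveal kidney failure.**
- The physician's baseline examination, which may or may not include a renal test.
- Existing care. Entry to heroin-assisted treatment is described as a situation "which for most patients is (far) more than a year ago", and the STUDY TREATMENTS section adds: "On a yearly basis, the treating physician and other treatment staff evaluate whether continuation of heroin-assisted treatment is indicated". That review is based on health and social functioning, and no renal test is mentioned.

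**Step 5. Timing.** The GENERAL STUDY DESIGN section already puts the steps in the right order: "Following screening and baseline assessment, eligible patients in a heroin-assisted maintenance treatment program will be randomly allocated". A baseline result can therefore be used before allocation without altering the sequence.

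**Step 6. Number of extra assays.** The planned size reproduces under the normal approximation. With a difference of 10 days, SD 17, two-sided alpha 0.10 and power 0.80:

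n = 2 × (1.645 + 0.842)² × 17² / 10² = 2 × 6.185 × 2.89 = 35.7, rounded up to 36 per group.

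The baseline assays for randomised patients are then 2 × 36 = 72, plus one for each screen failure. None of the inputs to this formula depends on the laboratory panel, so the sample size does not change.

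**The case against.** The strongest reply is that nothing in the Protocol is contradicted. Criterion 1 is a matter of clinical judgement, kidney failure is only an example in it, and it is applied through the physician's examination rather than the laboratory panel. Where a criterion depends on a test, as with the ECG, the Protocol says so. The examination and the exclusion checklist may well cover renal history. Candidates attend supervised treatment centres, most of them for a long time, so known severe kidney disease would probably be on record. The listed side effects include no renal item, and the summary of five earlier trials reports no renal event. Other exclusions, such as glaucoma, psychosis and lactation, have no dedicated test either, and no rule requires one for every named condition. Finally, the phrase pairing renal with kidney is redundant and may be a slip for liver or kidney.

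Much of this stands. The criterion is not unassessable, the group at risk is narrow, and no harm has been shown. The count of three in five is descriptive and does not amount to a breach of any standard.

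The factual core is unaffected. Neither the examination nor the yearly review is stated to include a renal test, and severe impairment is not always clinically evident. If the wording is a slip for liver or kidney, which is only inference, the liver half is matched by the enzymes in the panel and the kidney half remains unmeasured. The case for singling out kidney function over glaucoma is practical: one more assay on a sample already being drawn would measure it.

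**Conclusion.** The concern holds as a cheap improvement of minor weight. As written, the plan measures kidney function nowhere (0 of 10 analytes and no other scheduled test), although it excludes severe kidney failure and cites the blood panel in support of its safety conclusion.

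The residual risk is a patient with severe impairment that is unrecognised, clinically silent and missed at examination. The Protocol gives no figure from which to estimate how often that would occur, so no probability is offered; the number is likely to be small. No size of harm is claimed. The primary outcome, alpha, sample size and analysis are not affected.

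Two assumptions lie outside the text: that the assay is inexpensive, and that it can be run on the existing 16 ml sample. Both are reasonable, but neither is documented.

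**What to change.** Add serum creatinine with eGFR to the screening/baseline laboratory list under ASSESSMENTS, run on the sample already drawn. Require the result to reach the treating physician before the exclusion checklist in Table 1 is completed and before randomisation. Whether impairment counts as severe can remain the physician's judgement, or the investigator can write an eGFR limit into criterion 1. The Protocol gives no limit and none is proposed here. The wording that pairs renal with kidney could be tidied in the same edit.

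The cost is one routine assay per screened patient (72 for those randomised, plus screen failures), a few words in the text, and possibly a rare additional screen failure. No extra visit, puncture or staff is needed, and nothing in the design or analysis changes.
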